4.4. Identity of Investigational Product

International Non-proprietary name	eltrombopag
Manufacturer	GlaxoSmithKline (GSK)

Dose 200mg daily
Route of Administration oral
Formulation 50mg and 100mg tablets; in bottle

Eltrombopag will be provided by GSK

For oral administration only
Bottle containing 60 tablets of 100mg eltrombopag.
Store below 30 ⁰ C (86 ⁰ F). Do not refrigerate or freeze. Keep bottle tightly closed.
The Expiry date will provided via Certificate of Analysis prepared by GSK

4.5. Supportive Care Guidelines

4.5.1. Supportive measures including blood and platelet transfusions, antimicrobials, and analgesics are permitted.

4.5.2. The administration of anticancer therapies, other investigational cytotoxic agents, or prophylactic use of hematopoietic colony stimulating factors are not permitted.

4.5.3. Erythropoietin or hematopoietic colony stimulating factors for treatment of cytopenias are discouraged. If administered, the subject will not be eligible for a HI response assessment within one week of the receipt of epoetin alfa, filgrastim, or sargramostim, or for one month after receipt of pegfilgrastim or darbopoetin.

4.5.4. Platelet Transfusions: Platelet transfusion data must be captured on the case report form during the screening, treatment and extension periods. A unit of platelets is defined as a single unit of platelet-rich plasma or buffy-coat concentrate or 1 apheresis (single donor) concentrate. The number of units transfused must be recorded.

ASCO guidelines suggest platelet transfusion criteria of:

- Platelet count < 10 x 10⁹/L
- Signs of hemorrhage
- Subject with a high fever and platelet count < 20 x 10⁹/L
- Subject has a hyperleukocytosis
- There has been a rapid fall in platelet count and transfusions will not be readily available in case of emergencies

4.6. Duration of Therapy

Treatment is expected to continue until one of the following criteria applies:

- Lack of objective response after 2 cycles of therapy unless eltrombopag is considered to be of clinical benefit to the patient, or
- Clinically significant progressive disease, or
- Discontinuation of study drug for more than 6 weeks, or
- Intercurrent illness that prevents further administration of treatment, or
- Unacceptable adverse event(s), or
- Patient decision for study withdrawal, or
- General or specific changes in the patient's condition render the patient unacceptable for further treatment in the judgment of the investigator

Continuation of therapy beyond 12 months will be considered on a case-by-case basis for patients deriving clinical benefit after discussion with the PI and the discussion documented in the patient's medical record.

4.7 Dosing Delays/Dose Modifications

4.7.1 Dose adjustments for eltrombopag

The dose of eltrombopag will be adjusted according to the guidelines shown in the following tables for study drug-related clinically significant toxicity. If toxicity is not covered in the table, doses may be reduced or held at the discretion of the investigator for the patient's safety. See section 4.7.1.1. for additional liver chemistry stopping and follow-up criteria.

Patients will be withdrawn from the study if they fail to recover to CTCAE grade 0 to 1 (or within 1 grade of starting values for pre-existing laboratory abnormalities) from a clinically significant non-hematologic treatment-related toxicity within 6 weeks (leading to treatment delay of > 4 weeks) unless the investigator feels that the patient should remain in the study because of evidence that the patient is/may continue deriving benefit from continuing study treatment. Such instances will be discussed with the principal investigator on a case by case basis and the discussion documented in the medical record.

Patients with study-drug related toxicities that are manageable with supportive therapy may not require dose reductions. For patients with other drug-related toxicities, the following dose adjustment rules apply:

NCI CTCAE Grade	Action
Grade 0-2 non-hematological toxicity	No dose reduction. For grade 2 toxicities that are persistent and/or intolerable (e.g. stomatitis) patients may have a treatment interruption or dose reductions to the next lower dose level.
Grade 3-4 clinically significant non-hematological toxicity†	Hold until recover to NCI CTC AE grade 0-1 If recovery occurs within 2 weeks after treatment has been held, dose should be reduced to -1 dose level, if applicable.

† see 4.7.1.1. for additional liver chemistry stopping and follow-up criteria

Dose modifications for eltrombopag:

Dose level	eltrombopag (mg/day)
+1	300
0	200
-1	100
-2	50

4.7.1.1. Additional Liver Chemistry Stopping and Follow-Up Criteria:

If ALT $\geq 3x$ ULN and/or bilirubin $\geq 2x$ ULN, systematic evaluation for possible causes of hepatotoxicity must be initiated, with discontinuation of any potentially offending concomitant medications (in particular statins, antifungal agents, herbal supplements) and consideration of hepatobiliary imaging as appropriate. Subjects should return to clinic for repeat liver chemistries within 24-72 hours, and then at least weekly until liver chemistries (ALT, AST, alkaline phosphatase, bilirubin) resolve or stabilize.

Treatment should be held for any of the following liver chemistry criteria (all of which confer Grade III non-hematologic toxicity per NCI CTCAE):

1. ALT \geq 5x ULN and bilirubin \geq 2.7x ULN (>35% direct bilirubin)
2. ALT \geq 8x ULN
3. ALT \geq 5x ULN but < 8x ULN and persists for \geq 2 weeks
4. ALT \geq 5x ULN if associated with the appearance or worsening of symptoms of hepatitis such as nausea, vomiting, right upper quadrant pain or tenderness.
5. ALT \geq 5x ULN but < 8x ULN and cannot be monitored weekly for \geq 2 weeks.

When any of the above criteria is met, do the following:

- Immediately withdraw investigational product
- Report the event to Novartis Oncology within 24 hours of learning of its occurrence
- Complete the SAE data collection tool if the event also meets the criteria for an SAE. All events of ALT \geq 5x ULN and bilirubin \geq 2.7x ULN (>35% direct bilirubin), modified Hy's Law for oncology clinical trials²⁶, must be reported as an SAE.

NOTE: if serum bilirubin fractionation is not immediately available, study drug should be discontinued if ALT \geq 5x ULN and bilirubin \geq 2.7x ULN. Serum bilirubin fractionation should be performed if testing is available. If testing is unavailable, record the presence of detectable urinary bilirubin on dipstick, indicating bilirubin elevation and suggesting liver injury.

- Hold eltrombopag until recovery to NCI CTC AE grade 0-1 and restart at next lower dose level regardless of recovery time.

In addition, for #1:

- Make every reasonable attempt to have subjects return to clinic within 24 hours for repeat liver chemistries, liver event follow-up assessments (see below) and close monitoring.
- A specialist or hepatology consultation is recommended.
- Monitor subjects twice weekly until liver chemistries (ALT, AST, alkaline phosphatase, bilirubin) resolve, stabilize or return to within baseline values.

For #2, 3, 4, 5:

- Make every reasonable attempt to have subjects return to clinic within 24-72 hours for repeat liver chemistries and liver event follow-up assessments (see below)
- Monitor subjects weekly until liver chemistries (ALT, AST, alkaline phosphatase, bilirubin) resolve, stabilize or return to within baseline values.

For all Criteria 1-5, make every attempt to carry out the liver event follow-up assessments described below as clinically appropriate:

- Viral hepatitis serology (Hepatitis A IgM antibody; Hepatitis B surface antigen and Hepatitis B core antibody (IgM); Hepatitis C RNA; Cytomegalovirus IgM antibody; Epstein-Barr viral capsid antigen IgM antibody; Hepatitis E IgM antibody if subject resides outside the USA or Canada or has travelled outside the USA or Canada in the past 3 months).
- Serum creatine phosphokinase (CPK) and lactate dehydrogenase (LDH).

- Obtain complete blood count with differential to assess eosinophilia
- Record use of concomitant medications, acetaminophen, herbal remedies, other over the counter medications, or putative hepatotoxins.
- Record alcohol use
- Liver imaging (ultrasound, magnetic resonance, or computerized tomography) to evaluate liver disease.

4.7.1.2. Dose Adjustments Related to Platelet Count:

The starting dose for all study patients (with the exception of East Asians, see 4.7.1.3) will be 200mg orally daily. East Asians will start at 100mg orally daily. The eltrombopag dose can be increased by 100mg (to maximum of 300mg daily) after 2 weeks if the untransfused platelet count has not increased to $> 100 \times 10^9/L$ and the patient has not experienced any grade ≥ 3 study drug related toxicity. Laboratory work including a CBC with differential and blood chemistries including ALT, AST and bilirubin must be evaluated bi-weekly for 4 weeks after any change in eltrombopag dosing.

Eltrombopag will be held if platelet counts exceed $400 \times 10^9/L$, and will be resumed the next scheduled day that platelet counts have decreased to $\leq 100 \times 10^9/L$. Dose should be reduced to the next lower dose level, if appropriate.

Dose reductions or delays different than the dose described above are acceptable after discussion with the sponsor and the PI, and will require documentation of the rationale for such action.

4.7.1.3. Dose Adjustments for Subjects of East Asian Ancestry:

The starting dose for patients of East Asian ancestry will be 100mg orally daily. East Asian (i.e. Japanese, Chinese, Taiwanese and Korean) subjects exhibited 50-55% higher eltrombopag concentrations compared to non-East Asian subjects. Dose adjustments for platelet counts will proceed as per 4.7.1.2., regardless of ethnicity.

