4.7.2. Dosing for azacitidine and decitabine-related toxicities

Patients with drug-related toxicities that are manageable with supportive therapy may not require dose reductions. For patients with other drug-related toxicities, the following dose adjustment rules apply:

NCI CTCAE Grade	Action
Grade 0-2 non-hematological toxicity	No dose reduction. Grade 2 toxicities that are persistent and intolerable (e.g. stomatitis) can result in dose delays or dose reductions to the next lower dose level in Cycle 2 or beyond.

Grade 3-4 clinically significant non-hematological toxicity	Hold until recover to NCI CTCAE grade 0-1 If recovery occurs within 2 weeks after treatment has been held, dose should be reduced to –1 dose level, if applicable.
---	---

Standard dose reductions for azacitidine and decitabine are described in the following table (please note patients should start at the dose level they were receiving prior to study enrollment):

Dose level	Decitabine (in mg/m ² for 5 days)	Azacitidine (in mg/m ² for 7 days)
0	20	75
-1	15	50
-2	10	25
-3	10 for 4 days	25 for 5 days

Patients with delayed recovery of neutrophils to $1 \times 10^9/L$ and/or platelets to $75 \times 10^9/L$ in the absence of residual disease may have dose reductions by 1 dose level in subsequent cycles.

Patients with serious infectious complications in prior cycles may have the subsequent cycles administered at one dose level reduction in subsequent cycles.

Dose reductions or delays different than those described above are acceptable after discussion with the sponsor and the PI, and will require documentation of the rationale for such action.

4.7.3. For patients with adverse events that are due to one of the two agents, dose adjustments to only one of the study drugs may be adjusted as per the guidelines mentioned above.

4.7.4. For patients on Arm B, discontinuation of the hypomethylating agent and continued therapy with eltrombopag monotherapy after cycle 2 may be considered at the discretion of the investigator.

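### The eltrombopag rule for grade 3-4 non-hematological toxicity names level -1 (100 mg) as its destination, so a patient already on 100 mg gets no reduction as written

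*Combined protocol and SAP*

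**What the plan says.** Section 4.7.1 gives one numbered dose table for eltrombopag: +1 is 300 mg, 0 is 200 mg, -1 is 100 mg and -2 is 50 mg per day. The grade 3-4 non-hematological row requires a hold until grade 0-1 and then states: "If recovery occurs within 2 weeks after treatment has been held, dose should be reduced to -1 dose level, if applicable".

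The other three eltrombopag reduction rules are worded relative to the current dose:

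- Persistent or intolerable grade 2 toxicity (4.7.1): "patients may have a treatment interruption or dose reductions to the next lower dose level".
- Liver chemistry criteria (4.7.1.1): after recovery, "restart at next lower dose level regardless of recovery time".
- Platelets above 400 x 10^9/L (4.7.1.2): "Dose should be reduced to the next lower dose level, if appropriate".

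Section 4.7.1.3 adds: "The starting dose for patients of East Asian ancestry will be 100mg orally daily". It gives these patients no level numbering of their own. The only adjustment rule it mentions is the platelet-count rule, by reference to 4.7.1.2.

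**The concern.** The grade 3-4 row names a place in the table, where the other rules name a step. The two wordings agree only for a patient on the standard 200 mg start. A patient on 100 mg is already at the named place, so the written rule returns the dose that preceded the toxicity.

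This group includes every East Asian patient at the starting dose and any other patient previously reduced to 100 mg. What is at stake is the dose given to an individual patient after a serious drug-related event. Attributed, clinically significant events of grade 3 or higher are also the ones counted by the safety stopping rule in 8.3.1, so the restart dose after one of them should be unambiguous.

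**Working it through.** The plan states no figure to reproduce. The check is to look up each rule in the dose table.

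**Inputs.** The dose levels and the grade 2 and grade 3-4 rows come from 4.7.1, the liver rule from 4.7.1.1, the platelet rule and the 300 mg ceiling from 4.7.1.2, and the 100 mg East Asian start from 4.7.1.2 and 4.7.1.3.

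**Formula.** Reduction = (current dose - restart dose) / current dose.

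| Current dose | Grade 3-4 row, literal | Other three rules |
|---|---|---|
| 300 mg | 100 mg: 200/300 = 67% | 200 mg: 100/300 = 33% |
| 200 mg | 100 mg: 100/200 = 50% | 100 mg: 100/200 = 50% |
| 100 mg | 100 mg: 0/100 = 0% | 50 mg: 50/100 = 50% |

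**Reading the table.**

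1. At 200 mg the wordings coincide, so the problem does not show for a patient at the standard start.
2. At 100 mg the literal rule gives no reduction, and the other rules give 50 mg.
3. At 300 mg the literal rule is the stricter one, because it drops two levels. A wording change therefore also alters this row.
4. The literal rule never leads to level -2, although the table provides that level.
5. At 50 mg no lower level exists, so neither wording gives a reduced dose.

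**Scope.** The row's reduction sentence covers recovery within 2 weeks of the hold. Events that meet the liver criteria in 4.7.1.1 have their own clear rule. What remains is a grade 3-4 non-hematological event outside those criteria, in a patient on 100 mg.

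**The case against.** The strongest reply is that nobody would apply the row literally. It says the dose should be reduced, and going from 100 mg to 100 mg is not a reduction. The same phrase stands in the hypomethylating-agent table in 4.7.2, above levels that run to -3, which suggests loose shorthand for one level down. This stands as a reading of intent.

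There are also real safeguards. The hold until grade 0-1 is mandatory. Section 4.3.4 requires the PI or a representative to approve any dose change beforehand, and all patients are accrued from one center. Section 4.3.9 allows individual variations, and unacceptable adverse events end treatment (4.6). Section 4.7.1.2 adds: "Dose reductions or delays different than the dose described above are acceptable after discussion with the sponsor and the PI". These limit the harm, but none of them names 50 mg as the default. The words on applicability could equally mean that the reduction does not apply to someone already at level -1. The investigator discretion in 4.7.1 is for toxicity outside the table, and grade 3-4 toxicity is inside it. The PI would be interpreting the same row.

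Three stronger readings are tempting, and the documents do not support them.

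- *A grade 2 event is better protected than a grade 3-4 event.* The grade 2 rule is only permissive and applies to persistent or intolerable toxicity. The grade 3-4 rule requires a hold. Only the written restart dose is out of order.
- *East Asian patients are over-exposed and then denied a reduction.* Section 4.7.1.3 does say that these "subjects exhibited 50-55% higher eltrombopag concentrations compared to non-East Asian subjects", but the half-dose start already responds to that. If exposure is proportional to dose, which the documents do not state, 100 mg gives 0.5 x 1.50 to 0.5 x 1.55, or about 75% to 78% of non-East Asian exposure at 200 mg.
- *Arm B has the same fault for the hypomethylating agent.* Section 4.7.2 says "please note patients should start at the dose level they were receiving prior to study enrollment", so a patient could enter at level -1 and meet the same literal result. However, 4.1.2 also lets adjustments follow the package insert or the institution's standard of care, so the row is not the only route. This is a secondary point of consistency.

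**Conclusion.** The inconsistency is real and worth correcting. As written, the grade 3-4 row gives a patient on 100 mg a 0% reduction, where the protocol's other three eltrombopag rules give 50%. One level down was probably intended, so this is a drafting fault in a dosing-safety rule. It does not show a deliberate choice to withhold reduction.

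The reach is small. The documents do not say how many of the 46 patients will be East Asian or how many others will be reduced to 100 mg; either number may be zero. No endpoint, sample size, stopping boundary or error rate changes. The conclusion rests on two readings of the text: that the single table in 4.7.1 applies to all patients, and that level -1 means 100 mg there. Nothing in the protocol says otherwise.

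**What to change.** In the grade 3-4 row of 4.7.1, replace the destination wording with: *reduced to the next lower dose level (50 mg for a patient on 100 mg)*. If the literal two-level drop from 300 mg is wanted, write instead: *to 100 mg from 200 or 300 mg, and to 50 mg from 100 mg*. The choice matters, because the first version softens the written reduction at 300 mg from 67% to 33%. It would help to add what happens to a patient already on 50 mg. The matching row in 4.7.2 may be aligned for consistency.

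The cost is one phrase in one row, or in two if 4.7.2 is aligned, with no extra visits, tests or patients. Section 4.4 already lists 50 mg tablets. The bottle it describes holds 100 mg tablets, so supply of the smaller strength should be confirmed.

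The downside is lower dose intensity after toxicity in the few patients on 100 mg. Section 2.2 reports no platelet responses in the 50 mg and 100 mg cohorts of the AML phase I study (n=7), against two of seven patients at 200 mg.

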Given this scientific rationale, we propose to evaluate the safety and efficacy of eltrombopag in MDS patients with HMA-failure (as defined by persistent cytopenias or rising blast percentage on HMAs). The use of a parallel two-arm Phase II design will allow the evaluation of disease response with the addition of single-agent eltrombopag after HMA failure, as well as to the addition of eltrombopag with *continuation* of the hypomethylating agent to evaluate for additive or synergistic responses, as have been reported with lenalidomide in combination with azacitidine in MDS-azacitidine failures.²⁵ As thrombocytopenia $<100,000 \times 10^9/L$ is an independent and adverse prognostic factor for overall survival in MDS at all stages and given the primary eltrombopag mechanism of augmented megakaryopoiesis, this study will evaluate HMA-failure patients with a platelet count of $<100 \times 10^9/L$.

2.3. Eltrombopag Safety Profile:

2.3.1. Hepatotoxicity:

Eltrombopag may cause hepatotoxicity. In the controlled clinical trials in chronic ITP, one patient experienced Grade 4 (NCI Common Terminology Criteria for Adverse Events [NCI CTCAE] toxicity scale) elevations in serum liver test values during therapy with eltrombopag, worsening of underlying cardiopulmonary disease, and death. One patient in the placebo group experienced a Grade 4 liver test abnormality. Overall, serum liver test abnormalities (predominantly Grade 2 or less in severity) were reported in 11% and 7% of the eltrombopag and placebo groups, respectively. In the 3 controlled chronic ITP trials, four patients (1%) treated with eltrombopag and three patients in the placebo group (2%) discontinued treatment due to hepatobiliary laboratory abnormalities. Seven of the patients treated with eltrombopag in the controlled trials with hepatobiliary laboratory abnormalities were re-exposed to eltrombopag in the extension trial. Six of these patients again experienced liver test abnormalities (predominantly Grade 1) resulting in discontinuation of eltrombopag in one patient. In the extension study chronic ITP trial, one additional patient had eltrombopag discontinued due to liver test abnormalities (\leq Grade 3).

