In 2 controlled clinical trials in patients with chronic hepatitis C and thrombocytopenia, ALT or AST $\geq 3X$ ULN was reported in 34% and 38% of the eltrombopag and placebo groups, respectively. Most patients receiving eltrombopag in combination with peginterferon/ribavirin therapy will experience indirect hyperbilirubinemia. Overall, total bilirubin $\geq 1.5 X$ ULN was reported in 76% and 50% of patients receiving eltrombopag and placebo, respectively.

Current guidelines include measurement of serum ALT, AST, and bilirubin prior to initiation of eltrombopag, every 2 weeks during the dose adjustment phase, and monthly following establishment of a stable dose. If bilirubin is elevated, perform fractionation. Evaluate abnormal serum liver tests with repeat testing within 3 to 5 days. If the abnormalities are confirmed, monitor serum liver tests weekly until the abnormality(ies) resolve, stabilize, or return to baseline levels. Discontinue eltrombopag if ALT levels increase to $\geq 3X$ (ULN) in patients with normal liver function or $\geq 3X$ baseline in patients with pre-treatment elevations in transaminases and are:

- progressive, or
- persistent for ≥ 4 weeks, or
- accompanied by increased direct bilirubin, or
- accompanied by clinical symptoms of liver injury or evidence for hepatic decompensation.

Reinitiating treatment with eltrombopag is not recommended. If the potential benefit for reinitiating treatment with eltrombopag is considered to outweigh the risk for hepatotoxicity, then cautiously reintroduce eltrombopag and measure serum liver tests weekly during the dose adjustment phase. If liver tests abnormalities persist, worsen or recur, then permanently discontinue eltrombopag.

2.3.2. Bone Marrow Reticulin Formation and Risk for Bone Marrow Fibrosis:

Eltrombopag is a thrombopoietin (TPO) receptor agonist and TPO-receptor agonists may increase the risk for the development or progression of reticulin fiber deposition within the bone marrow.

In the ITP extension study, seven patients had reticulin fiber deposition reported in bone marrow biopsies, including two patients who also had collagen fiber deposition. The fiber deposition was not associated with cytopenias and did not necessitate discontinuation of eltrombopag. However, clinical studies have not yet excluded a risk of bone marrow fibrosis with cytopenias.

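### The dose-increase rule in 4.7.1.2 sets no liver criterion, so it does not exclude a patient under the mandatory hepatotoxicity evaluation of 4.7.1.1

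*Combined protocol and SAP*

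**What the plan says.** Section 4.7.1.2 of the combined protocol and SAP states: "The eltrombopag dose can be increased by 100mg (to maximum of 300mg daily) after 2 weeks". Two conditions apply. Untransfused platelets must not have risen above 100 × 10⁹/L, and "the patient has not experienced any grade ≥ 3 study drug related toxicity". The section mentions liver tests only as monitoring after a dose change.

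Section 4.7.1.1 covers ALT ≥3× ULN and/or bilirubin ≥2× ULN. At that level "systematic evaluation for possible causes of hepatotoxicity must be initiated", and suspect co-medications are to be stopped. "Subjects should return to clinic for repeat liver chemistries within 24-72 hours, and then at least weekly until liver chemistries" resolve or stabilize. Dosing is held only under five listed criteria, described as "all of which confer Grade III non-hematologic toxicity per NCI CTCAE". All five need ALT of 5× ULN or more.

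Neither section refers to the other on the subject of raising the dose.

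**The concern.** The evaluation in 4.7.1.1 exists to find out whether eltrombopag or something else caused the liver signal. Raising the dose before that is known adds exposure to one of the candidate causes. It also blurs the evaluation: if a suspect co-medication is stopped and eltrombopag is increased together, a later change in ALT could reflect either.

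The escalation condition starts at grade 3, above the level at which the protocol itself requires a work-up. It also sits above most of the liver signal described for the drug. In the controlled ITP trials (2.3.1), "serum liver test abnormalities (predominantly Grade 2 or less in severity) were reported in 11% and 7% of the eltrombopag and placebo groups". The condition further requires that the toxicity be drug-related, which is the question the evaluation is meant to settle.

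**Working it through.** No sample size, power or error rate bears on this point. The check sets thresholds and timing side by side.

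**1. Thresholds**

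| Liver finding | Evaluation required (4.7.1.1)? | Hold criterion met? | Excluded from an increase by 4.7.1.2? |
|---|---|---|---|
| ALT 3 to <5× ULN | Yes | No | No |
| Bilirubin ≥2× ULN, ALT <5× ULN | Yes | No | Only if graded ≥3 and attributed to study drug |
| ALT 5 to <8× ULN, no hold criterion met | Yes | No | Yes, if attributed to study drug |
| Any of criteria 1–5 | Yes | Yes | Yes, drug is held |

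The protocol does not reproduce the CTCAE cut-offs. That ALT 3 to <5× ULN lies below grade 3 is inferred from 4.7.1.1 calling its ≥5× criteria Grade III. The grade of an isolated bilirubin ≥2× ULN is not stated.

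**2. Other clauses that might supply the bar**

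- 4.3.4: the principal investigator or a representative must approve each dose change in advance. No liver criterion is attached.
- 4.7.1: the investigator may hold or reduce for toxicity outside the table. Increases are not addressed.
- 4.7.1.2: bi-weekly chemistries for four weeks, but after the change.
- 2.3.1: recites guidance to discontinue at ALT ≥3× ULN (or ≥3× an elevated baseline) if the rise is progressive, persistent, or accompanied by raised direct bilirubin or symptoms. It does not address escalation.
- 8.3: the Bayesian toxicity rule acts on a whole arm and counts only attributed grade ≥3 events.

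**3. Timing** (nominal days, first dose on Day 1)

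The study calendar draws liver chemistries on Days 8, 15 and 22 of cycle 1. An increase is allowed from about Day 15. A Day 15 signal is due for repeat on Days 16–18, after the dose may already have risen. A Day 8 signal has its repeat on Days 9–11 and its next weekly test around Days 16–18, so it too can still be open on Day 15.

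**4. What waiting costs, for a Day 15 signal**

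Cycle 2 ends on Day 2 × 28 = 56 and cycle 6 on Day 6 × 28 = 168. Without delay, 56 − 15 = 41 and 168 − 15 = 153 days remain at the higher dose.

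| Signal clears at | Delay (days) | Left to end of cycle 2, longest delay | Share of 41 days lost | Left to end of cycle 6 |
|---|---|---|---|---|
| 24–72 h repeat (Day 16–18) | 1–3 | 56 − 18 = 38 | 3/41 = 7% | 150 |
| Next weekly test (Day 23–25) | 8–10 | 56 − 25 = 31 | 10/41 = 24% | 143 |
| Second weekly test (Day 30–32) | 15–17 | 56 − 32 = 24 | 17/41 = 41% | 136 |
| Four weeks (Day 43) | 28 | 56 − 43 = 13 | 28/41 = 68% | 125 |

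**5. How often, and how large a step**

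The documents give no rate of ALT 3 to <5× ULN or bilirubin ≥2× ULN at 200 mg in MDS. Indirect figures from 2.3.1, eltrombopag minus placebo:

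- ITP, any liver test abnormality: 11 − 7 = +4 points.
- Hepatitis C, ALT or AST ≥3× ("ULN was reported in 34% and 38% of the eltrombopag and placebo groups"): 34 − 38 = −4 points.
- Hepatitis C, total bilirubin ≥1.5× ULN: 76 − 50 = +26 points, in patients on peginterferon/ribavirin, most of whom are expected to have indirect hyperbilirubinemia.

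One step is 200 to 300 mg (+50%), or 100 to 200 mg (+100%) in East Asian patients. With the 50–55% higher concentrations in 4.7.1.3, 200 mg corresponds to 200 × 1.50 to 1.55 = 300–310 mg in other patients, if exposure is dose-proportional (assumption).

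**The case against.** The strongest reply is that a missing prohibition is not an instruction. The increase is optional, and someone with authority has to approve it first. Platelets and liver tests are drawn at the same visits, so the approver would ordinarily have the first raised value in hand. After an increase, the weekly tests and hold criteria 1–5 still apply. The grade 3 threshold also matches the rest of the plan, which acts on dose at grade 3–4 (4.7.1) and monitors attributed grade ≥3 events (8.3). The closest match to the ALT trigger shows no excess over placebo, and the phase I AML study in 2.2 treated nine patients at 300 mg without reaching a maximum tolerated dose. Delay has a price too: 4.6 and 8.2.1 both look at response within two cycles, and 2.1 cites median survival of 4 to 5.6 months.

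Most of this stands, and it limits the weight of the point. It does not supply the missing criterion: each safeguard leaves the liver threshold for escalating to case-by-case judgement. The record at 300 mg is also not wholly clean. Section 2.2 reports a dose-limiting toxicity that included raised liver enzymes at that dose, among 11 patients given eltrombopag with azacitidine. That is one confounded case and shows no rate.

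A reader might infer that the protocol directs escalation into a liver signal, or contradicts itself. The documents do not support that: the wording is permissive and prior approval is required. A reader might also extend the gap to ALT ≥5× ULN generally. That goes too far, because 4.7.1.1 treats its ≥5× criteria as Grade III, and in the 5 to <8× band the gap opens only while no hold criterion is met and attribution is undecided.

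**Conclusion.** The concern holds in a limited form. The written escalation rule does not exclude a patient with ALT 3 to <5× ULN, or with bilirubin ≥2× ULN and ALT <5× ULN, who is under a mandatory hepatotoxicity evaluation. Existing safeguards reduce the risk, but none states a liver criterion for increasing the dose.

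Severity is minor and the change is a cheap improvement. The number of patients affected cannot be estimated from the documents, and no statistical figure depends on it. A reader might infer that the plan exposes patients to a known excess of such events. The documents show no such excess in ALT at the 3× level, and their bilirubin figure uses a lower threshold in a different treatment setting.

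The conclusion assumes that ALT 3 to <5× ULN is below grade 3, as 4.7.1.1 implies. The bilirubin limb assumes that the event is graded below 3 or is not attributed to study drug. The day counts assume nominal visits and undelayed 28-day cycles.

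**What to change.** Add to 4.7.1.2:

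> Do not increase the dose while ALT is ≥3× ULN (or, if elevated at baseline, above the baseline value) or direct bilirubin is raised above baseline, regardless of attribution. After any 4.7.1.1 trigger, do not increase until at least the 24–72 hour repeat has been reviewed by the PI and shows values below these limits. Isolated indirect hyperbilirubinemia, including Gilbert's disease, does not by itself bar an increase.

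Leave hold criteria 1–5 unchanged. A numeric limit is preferable to a bar that lifts when the evaluation closes: 4.7.1.1 does not define stabilization, so a steady ALT of 4× ULN could count as closed. A baseline clause is needed because entry (3.1) allows ALT or AST up to 3× ULN and bilirubin up to 2× ULN, which are the trigger values themselves (3 − 3 = 0; 2 − 2 = 0). As worded, the clause is strict for patients entering with a mildly raised ALT, since any rise above that value bars an increase. The sponsor should confirm that this is wanted.

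Cost: one protocol amendment, one documented review by the principal investigator, and no new visits, because the repeat tests are already required. Fractionated bilirubin is needed when total bilirubin is raised, which 2.3.1 already advises ("If bilirubin is elevated, perform fractionation"). Screening lists only total bilirubin, so where no baseline direct value exists the laboratory's upper limit could serve. The main downside is delay: 1–3 days if the first repeat clears and longer if values stay raised. A patient who never falls below the limits would not be escalated at all. Any such delay shortens time at the higher dose before the two-cycle assessment.
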